##### **11.4.1 Analysis Population**

All lesions identified by  $^{68}\text{Ga}$ -NeoBOMB1 PET/MRI and  $^{68}\text{Ga}$ -PSMA R2 PET/MRI.

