### **5.2 Details of Imaging (ie, dynamic, static, number of scans, etc.)**

A localizer MRI scan will be performed at 45 minutes after injection of 150 to 250 MBq of Ga-NeoBOMB1 (or Ga-PSMA R2, depending on randomization) to define the table positions. After correct positioning of the spatial acquisition windows is ensured, the combined PET/MRI acquisition will be initiated with 3–5 table positions at a 4-min acquisition time per table position. A volumetric T1 acquisition with fat-water separation and motion correction to enable free-breathing will be obtained at each table position and used for the generation of attenuation maps and for anatomic allocation of the PET results. Simultaneously with the start of the T1 MRI sequence, the PET acquisition will start at the same table position, thus ensuring optimal temporal and regional correspondence between MRI and PET data. The PET acquisition time will be 4 min per table position, taking delayed acquisition times and radioactive decay into account. As the T1 will take less than 4\ minutes, a rapid diffusion weighted MRI will also be performed. After completion of the PET acquisition, the table will be moved to the next table position and the procedure will be repeated. Upon completion of the PET acquisition for all stations, volumetric post-contrast T1- and T2-weighted MR images may be obtained at multiple stations as needed.

A localizer MRI scan will be performed at 45 minutes after injection of 150 – 250 MBq of Ga-PSMA R2 (or Ga-NeoBOMB1, depending on randomization) to define the table positions. After correct positioning of the spatial acquisition windows is ensured, the combined PET/MRI acquisition will be initiated with 3–5 table positions at a 4-min acquisition time per table position. ----Only MR sequences required for attenuation correction of PET data will be acquired.

Participants will be randomized to have Ga-NeoBOMB1 first followed by Ga-PSMA R2 within 2 weeks or Ga-PSMA R2 first followed by Ga-NeoBOMB1 within 2 weeks (50/50 chance for each schedule).

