## **10.2 Measurement Methods**

PET images will be interpreted using the AW software (GE Healthcare) and the location of uptake will be recorded for each patient, blinded to the results of other studies. MR images will be evaluated for detection of areas of abnormal signal or anatomical structures, blinded to the results of PET or other studies.

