## **11. STATISTICAL CONSIDERATIONS**

### **11.1 Statistical Design**

Prospective single center, single-arm study. Patients will be scanned with Ga-NeoBOMB1 PET/MRI and Ga-PSMA R2 PET/MRI. MRI and PET/MRI scans will each be evaluated separately by two readers.

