#### **11.4 Key variables**

Reference standard: disease status of a lesion will be defined by biopsy of suspicious lesions, when clinically feasible. 12-months clinical follow-up with imaging will be gold standard if biopsy cannot be done.

Test to be evaluated:  $^{68}\text{Ga}$ -NeoBOMB1 and  $^{68}\text{Ga}$ -PSMA R2 positivity will be determined by the operator as uptake more than the adjacent background (malignant) or less (benign). Visual conspicuity against background on the diffusion weighted images and presence of an anatomically corresponding abnormality on the T1w and T2w images are the criteria for detecting a lesion on MRI.

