##### **11.4.2 Analysis Plan**

- Sensitivity, specificity, and positive and negative predictive value of imaging modalities will be estimated.
- Sensitivity and specificity of PET/MRI and MR alone will be compared by McNemar tests of paired proportions.
- The number and type of discrepancies between  $^{68}\text{Ga}$ -NeoBOMB1 and  $^{68}\text{Ga}$ -PSMA R2 will be tabulated.
- We will explore hypotheses about the reasons for such discrepancies, such as PSA level/velocity, Gleason score, and location.

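### Section 11.4.1 leaves the blinded MR-alone read out of the lesion set; read plainly, this drops malignant MR-only lesions and tilts the McNemar comparison towards PET/MRI, by an amount the documents do not fix

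*Combined protocol and SAP*

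**What the plan says.** Section 11.4.1 gives the analysis population as "All lesions identified by" NeoBOMB1 PET/MRI and PSMA R2 PET/MRI. MR alone is not mentioned there, but elsewhere it is a full comparator:

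- Section 10.1 makes PET/MRI against MR alone the principal goal and counts lesions on conventional MR.
- Section 10.2: "MR images will be evaluated for detection of areas of abnormal signal or anatomical structures, blinded to the results of PET or other studies".
- Section 11.1: "MRI and PET/MRI scans will each be evaluated separately by two readers".
- Section 11.4 gives MR its own detection criteria (diffusion conspicuity with a T1w/T2w correlate). For the tracers, "positivity will be determined by the operator as uptake more than the adjacent background (malignant) or less (benign)".
- Section 11.4.2: "Sensitivity and specificity of PET/MRI and MR alone will be compared by McNemar tests of paired proportions", and "Sensitivity, specificity, and positive and negative predictive value of imaging modalities will be estimated".
- Section 11.5 powers a per-lesion comparison of about 40% (MR) with about 60% (PET).

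No section says whether a lesion seen only on the MR-alone read belongs to the set.

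**The concern.** McNemar's test uses only the two discordant cells: PET-positive/MR-negative and PET-negative/MR-positive. A blinded MR read can produce lesions of the second kind. If a lesion must be positive on a tracer scan to enter the set, the effect depends on how PET is defined:

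- **Pooled PET, or one tracer on its own lesions.** The MR-favouring cell is empty by definition and PET sensitivity is 100% whatever the truth.
- **One tracer in the union of both tracers' lesions.** The cell keeps only those lesions that the other tracer found.

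In both cases the loss is one-sided, so the test can declare PET/MRI more sensitive when the two are equal. This is the only comparison with a power statement. Specificity and negative predictive value suffer too. In a PET-positive set every reference-negative lesion is a PET false positive, so pooled PET specificity is 0 (or undefined if there are none) and its negative predictive value is undefined.

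**Working it through.** **The plan's own figure.** Section 11.5 states 90% power, one-sided 5%, N = 50, 40% against 60%. Let c be the share of malignant lesions that are MR-positive and PET-negative, and b = c + 0.20. The paired normal approximation is Φ((0.20√50 − 1.645√(b+c)) / √(b+c−0.04)). It gives 0.955 at c = 0, 0.913 at 0.02, 0.890 at 0.03 and 0.629 at 0.16. The 90% is reproduced only for c of about 0.02 to 0.03, a value the plan does not state.

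**Inputs for the bias.** From the plan: 60% and 40% sensitivity, one-sided 5%, 50 lesions (11.5), and about 2/3 same findings (11.3). Assumed: the 2/3 applies per lesion; lesions are independent; MR is independent of the other tracer among lesions that the tested tracer missed; and the MR-only share q (malignant lesions seen by MR and missed by the PET result under test, as a share of all malignant lesions). The value q = 24% is independence at 60/60, 0.6 × 0.4. The other values only span a range.

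**False rejection when both true sensitivities are 60%.** The discordant cells are then equal, q each, among all malignant lesions.

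- *Own-lesion or pooled set.* Cells are q/0.6 and 0. With the second cell empty, the exact test rejects at 5 or more discordant lesions (0.5⁵ = 0.031; 0.5⁴ = 0.063). Rejection is P(Bin(50, q/0.6) ≥ 5) for 50 malignant lesions in the set, or P(Bin(50, q) ≥ 5) for 50 in total.
- *Single tracer, union set.* Let u be the share found by either tracer and f the chance that the other tracer finds a lesion the tested one missed. Cells are q/u and fq/u. With 2/3 overlap, (1.2 − u)/u = 2/3 gives u = 0.72 and f = 0.12/0.4 = 0.3. With independent tracers, u = 1 − 0.4² = 0.84 and f = 0.6.

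| Lesion set | q = 2.6% | 5% | 10% | 24% |
|---|---|---|---|---|
| Own-lesion or pooled, 50 in set | 6.5% | 41% | 94% | >99.9% |
| Own-lesion or pooled, 50 in total | 1% | 10% | 57% | 99.7% |
| Own-lesion or pooled, 20 in set | 0.1% | 2% | 23% | 95% |
| Union of 50, 2/3 overlap | 2% | 12% | 35% | 78% |
| Union of 50, independent tracers | 1% | 4% | 11% | 26% |
| All malignant lesions kept, 50 | 0.3% | 1.2% | 2.3% | 3.3% |
| Tracer- or MR-positive lesions, PET scored by uptake, 50 | 0.9% | 1.9% | 2.9% | 3.5% |

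The first row passes 5% at q of about 2.5%.

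**Apparent gap at the planned 60/40.** Here q runs from 0 to 16% (independence, 0.4 × 0.4). The right comparison is with the same set after MR-only lesions are added.

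| Set | Restricted | MR-only lesions added |
|---|---|---|
| Own-lesion or pooled | 1 − (0.4 − q)/0.6 = 33 to 60 points | 0.2/(0.6 + q) = 33 to 26 |
| Union, 2/3 overlap | (0.2 + q − fq)/u = 28 to 43 | 0.2/(u + q(1 − f)) = 28 to 24 |
| Union, independent | 24 to 31 | 24 to 22 |

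The restriction therefore adds 0 to 34, 0 to 19 or 0 to 9 points. At q = 0 it adds nothing.

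**The case against.** The strongest reply is that 11.4.1 means the hybrid examination: lesions seen on its MR part enter the set, and PET is then scored by uptake. Several passages point that way. The calendar in section 7 lists no separate MR exam. The MR criteria in 11.4 match sequences taken during the PET/MRI (section 5.2: "a rapid diffusion weighted MRI will also be performed"). The low-uptake category in 11.4 presupposes lesions that enter without uptake, and 11.4.2 plans specificity and negative predictive value. On this reading the MR-favouring cell is filled and the test is not inflated.

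This makes the reading plausible but does not settle it, because the plan does not state it. It also needs a further unstated rule. For the second scan section 5.2 says "Only MR sequences required for attenuation correction of PET data will be acquired", so lesions from the exam with diffusion images would have to count for both tracers. And if a lesion seen on the MR part were itself counted as detected by PET/MRI, the cell would be empty again.

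A reader might take the 60% in 11.5 as proof of one reading. It is not. On the plain reading pooled PET sensitivity is 100%. On the hybrid reading it is 0.6/(0.6 + q), which is 100% at q = 0 and 79% at q = 16%. Neither gives 60%.

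A second reply is that q may be small. That stands: near the c that reproduces the 90% power, false rejection is 6.5% at most. That c belongs to the 60/40 scenario, however, and is only a guide.

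**Conclusion.** The concern holds as a defect in the definition of the lesion set. Followed as written, 11.4.1 biases the lesion-level test towards PET/MRI whenever some malignant lesions are MR-only. The direction is clear on the plain reading. The size is not, because it depends on q, on whether PET is pooled or taken per tracer, and on whether 50 counts lesions in the set or in total. At q = 5% false rejection runs from 4% to 41% across the 50-lesion versions; with MR-only lesions included it is at most 3.5% at every q examined.

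Three stronger inferences are not supported. The 94% and >99.9% figures are not expected error rates, since nothing in the documents gives a q of 10% or 24%. The whole excess over the planned 20 points is not due to this rule: at q = 0 the 33-point gap comes from lesions missed by every method, which no definition of the set recovers. And the trial's named outcomes are not undermined: the per-patient lesion counts (10.1) and the share of detected lesions confirmed malignant (10.4) do not use this set comparison.

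Confidence is moderate, because the hybrid reading is plausible. The point should be fixed before analysis, so that the reading is not chosen with the data in view.

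**What to change.** Change 11.4.1 to: all lesions identified by NeoBOMB1 PET/MRI, PSMA R2 PET/MRI or the blinded MR-alone read, each scored present or absent on every method, with PET scored by the uptake rule in 11.4. In 11.4.2:

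- Compare sensitivity among reference-positive lesions and label it relative sensitivity, because lesions missed by every method remain unknown.
- Report the number of unverified lesions by detecting method.
- Label lesion-level specificity and negative predictive value as conditional on detection.

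The cost is one sentence in 11.4.1, these labels and some extra tabulation; the MR reads and MR lesion counts are already planned. The apparent PET advantage will be smaller and power lower than on the restricted set. Some MR-only lesions may lack verification, because follow-up under 6.3 is chart review of standard-of-care results.

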##### **11.4.2 Analysis Plan**

- Sensitivity, specificity, and positive and negative predictive value of imaging modalities will be estimated.
- Sensitivity and specificity of PET/MRI and MR alone will be compared by McNemar tests of paired proportions.
- The number and type of discrepancies between  $^{68}\text{Ga}$ -NeoBOMB1 and  $^{68}\text{Ga}$ -PSMA R2 will be tabulated.
- We will explore hypotheses about the reasons for such discrepancies, such as PSA level/velocity, Gleason score, and location.

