#### **11.5 Sample size justification**

The following estimate is for a per-lesion analysis. We expect approximately 70% of patients (~35) to have one or more PET-positive findings and approximately 1/3 to be biopsied. Our existing data for  $^{68}\text{Ga}$  PSMA-11 and  $^{68}\text{Ga}$ -RM2 (please see attached publications) indicate no false positive findings based on biopsy. We cannot predict an average number of lesions per patient given small data available to date, but if only half of the positive patients have more than one lesion, this will easily yield 50 lesions. We also expect the sensitivity of MR alone to be roughly 40%, while that of PET to be roughly 60% or more. A sample size of 50 patients will provide 90% power at one-sided 5% error to detect such a difference. Participants who complete only one PET/MRI scan (either due to withdrawal of consent or loss to follow-up) will not be replaced with additional subjects.

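### Per-lesion sensitivity is planned on lesions the tracer scans already found, so lesions both tracers missed cannot count against PET: a true 60% could read as about 71% to 83%

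*Combined protocol and SAP*

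**What the plan says.** Section 11.4.2 (Analysis Plan) promises accuracy estimates and a paired comparison: "Sensitivity, specificity, and positive and negative predictive value of imaging modalities will be estimated" and "Sensitivity and specificity of PET/MRI and MR alone will be compared by McNemar tests of paired proportions".

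Section 11.4.1 (Analysis Population) gives the only analysis set. It begins "All lesions identified by" and names the two tracer PET/MRI scans. MR alone is not mentioned.

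Section 11.5 (Sample size justification) fixes the unit, "The following estimate is for a per-lesion analysis", and the planning values: "We also expect the sensitivity of MR alone to be roughly 40%, while that of PET to be roughly 60% or more". Its lesion count starts from the men with a positive scan: "We expect approximately 70% of patients (~35) to have one or more PET-positive findings and approximately 1/3 to be biopsied".

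Section 11.4 sets the reference standard: biopsy of suspicious lesions where feasible, otherwise 12 months of clinical follow-up with imaging. Section 6.3 describes that follow-up as a chart review of standard-of-care biopsies and imaging.

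**The concern.** Sensitivity is the share of all malignant lesions that a test finds, so its denominator must include the lesions the test missed. Here a lesion enters the denominator only if one of the two tracers showed it. A tracer can be charged with a miss only where the other tracer succeeded, and no miss shared by both is ever counted. The roughly 15 of 50 men expected to have no PET finding (50 − 35) all met the PSA criterion for recurrence, yet they add nothing to this denominator.

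At stake are the sensitivity estimates promised in Section 11.4.2 and the PET-minus-MR difference. Readers would naturally set both against the 40% and 60% of Section 11.5, which are meaningful only as shares of all malignant lesions.

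**Working it through.** **Inputs**
- MR 40%, PET 60% (Section 11.5). I apply 60% to each tracer, because the section does not separate them.
- About 35 of 50 men PET-positive, half of them with more than one lesion (Section 11.5).
- About two-thirds same and one-third different findings (Section 11.3, carried over from another tracer pair). Reading this per lesion and splitting the discordant third equally are my assumptions.
- Overlap between PET and MR: not stated. I use independence and then show the limits.
- All lesions in the set are taken as malignant, for simplicity.

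**The plan's own figures**

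*Lesion count.* If each man with more than one lesion has exactly two (an assumption), then 17.5 × 1 + 17.5 × 2 = 52.5. This matches the planned 50, and it counts lesions in PET-positive men only.

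*Power.* The plan says: "A sample size of 50 patients will provide 90% power at one-sided 5% error to detect such a difference". For a one-sided McNemar test with n = 50 pairs and discordant share ψ, power = Φ[(0.2√50 − 1.645√ψ)/√(ψ − 0.04)].
- ψ = 0.25: (1.414 − 0.822)/0.458 = 1.29, power 90.2%.
- ψ = 0.52 (independence): (1.414 − 1.186)/0.693 = 0.33, power 62.9%.

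So 90% is reproducible at about 25% discordance, which the plan does not state. The calculation takes 40% and 60% as given and does not address how lesions enter the set.

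**Formula**

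Let U be the share of all malignant lesions found by at least one scan that defines the set. A tracer with true sensitivity S, whose findings all lie in the set, reads S/U.

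**Results for a true 60% per tracer and 40% for MR**

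| Lesion set and overlap | U | Tracer reads | MR reads | Gap |
|---|---|---|---|---|
| Section 11.4.1, independent | 1 − 0.4² = 0.84 | 0.60/0.84 = 71.4% | 40% | 31.4 points |
| Section 11.4.1, 2/3 shared | 0.60/(2/3 + 1/6) = 0.72 | 83.3% | 40% | 43.3 points |
| Both tracers plus independent MR, tracers independent | 1 − 0.4² × 0.6 = 0.904 | 66.4% | 44.2% | 22.1 points |
| Both tracers plus independent MR, 2/3 shared | 1 − 0.28 × 0.6 = 0.832 | 72.1% | 48.1% | 24.0 points |

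In the first two rows MR stays at 40% because, under independence, MR finds 40% of any set that was chosen by the tracers.

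**Limits.** If the scans together miss nothing, U = 1 and the tracer reads 60%. If detection is fully nested, U = 0.60 and it reads 100%. A lesion positive on either tracer is in the Section 11.4.1 set by definition, so pooled PET reads 100% whatever the overlap.

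**The gap without an overlap assumption.** MR cannot read more than 0.40/U, so the gap is at least (0.60 − 0.40)/U = 0.20/U. It exceeds 20 points whenever U is below 1. On the union of all reads it equals 0.20/U, and the ratio stays at 0.60/0.40 = 1.5.

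**McNemar cells.** Lesions missed by every read fall in the double-negative cell, which the test ignores. On the Section 11.4.1 set under independence, however, the tracer-negative, MR-positive cell falls from 0.4 × 0.4 = 16% of true lesions to 0.4 × 0.4 × 0.6 = 9.6%. The tracer-positive, MR-negative cell stays at 0.6 × 0.6 = 36%. That imbalance comes from leaving out lesions seen on MR only.

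**The case against.** **The follow-up will reveal missed lesions.** Sections 6.3, 10.1 and 11.4 do provide 12 months of biopsy and imaging data, and some missed lesions will surface there. But Section 11.4.1 does not add them, and nothing says how a missed lesion would be told from a new one. The follow-up is a possible source for a better denominator; the plan does not use it as one.

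**PET/MRI includes the MR component.** On that reading MR findings enter the set and the third and fourth rows of the table apply. The inflation shrinks, but lesions missed by every read are still absent.

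**The planned test is not affected.** This stands for lesions missed by all reads, once MR-only lesions are in the set. The harm is then to the estimates and the difference, not to the McNemar result.

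**The named outcomes do not need undetected lesions.** This also stands. The primary outcome (Section 10.1) is the number of lesions detected per patient. The secondary outcome (Section 10.4) is the percentage of detected lesions confirmed malignant, which properly conditions on detection. A reader might infer that men with no lesion drop out of the per-patient figures, but Section 10.1 reports per patient and nothing suggests that they do.

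**Conclusion.** The point holds for the sensitivity estimates of Section 11.4.2 and for the PET-minus-MR difference. Followed as written, the plan gives tracer sensitivities that are too high whenever both scans miss a malignant lesion, and a pooled PET sensitivity that cannot fall below 100%. The illustrative sizes rest on a true 60% for each tracer, independent MR detection, and either independent tracers or the two-thirds concordance read per lesion. Only the direction, the outer limits and the 0.20/U bound are free of the overlap assumptions.

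Three stronger readings are tempting but not supported:
- That a true 60% would read as 79% or more. That figure is 0.60/0.76, where 0.76 = 1 − 0.4 × 0.6 is the union of one PET scan and MR with independent misses. It is not the Section 11.4.1 set, and it is not a floor.
- That every modality is inflated and the PET:MR ratio is kept on any set. This is true on the union of all reads. On the Section 11.4.1 set with independent detection MR reads 40% and the ratio is 71.4/40 = 1.8 to 83.3/40 = 2.1.
- That every man without a PET finding has a missed lesion. The documents establish biochemical recurrence in these men, not a lesion count.

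This should be fixed before analysis. It does not undermine the primary or secondary outcome.

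**What to change.** - **Section 11.4.1:** define the lesion set as the union of lesions found by any read, that is, either tracer PET/MRI or MR alone.
- **Section 11.4.2:** replace absolute lesion-level sensitivity with relative sensitivity. For each tracer this is the number of verified true-positive lesions on its PET/MRI divided by the number on MR alone, in men who had that tracer scan. The unknown number of lesions missed by all reads cancels from this ratio. Keep the paired comparison, on this set.
- **Section 11.4.2:** report absolute detection per patient, with every man scanned with that tracer in the denominator. This makes explicit what Section 10.1 already implies.
- **Section 11.5:** state that 40% and 60% are planning values for all malignant lesions, which the scan-detected set cannot estimate.

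The cost is wording in three sections and no new data. The price is that no absolute lesion-level sensitivity is reported, and the apparent PET figure is less favourable.

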### **10.4 Secondary Outcome Measure**

- Secondary Outcome measure: Predictive value of malignancy
- Timeframe: After 1 year clinical follow-up
- Description: The predictive value of Ga- NeoBOMB1 PET/MRI and Ga-PSMA R2 PET/MRI imaging will be evaluated based on biopsy and/or imaging results during 12 month standard clinical follow-up. Outcome will be reported as- percentage of detected lesions that were confirmed to be malignant for each imaging method.

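### The per-lesion McNemar test treats several lesions from one man as independent; if PET-minus-MR differences correlate within a man, the one-sided 5% error can be exceeded, modestly in the plan's minimum scenario and more with more lesions per man.

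*Combined protocol and SAP*

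**What the plan says.** Section 11.4.2 names one statistical test: "Sensitivity and specificity of PET/MRI and MR alone will be compared by McNemar tests of paired proportions". It does not say whether the exact or the asymptotic version is meant, and the sentence itself does not name the unit.

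The unit comes from the neighbouring sections:

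- 11.4 (reference standard): "disease status of a lesion will be defined by biopsy of suspicious lesions, when clinically feasible".
- 11.4.1 (analysis population): the set begins "All lesions identified by" and goes on to the two PET/MRI scans.
- 11.5 (sample size): "The following estimate is for a per-lesion analysis".
- 10.4 (secondary outcome): "percentage of detected lesions that were confirmed to be malignant for each imaging method".

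Section 11.5 expects about 35 of 50 patients to have PET-positive findings. It says "We cannot predict an average number of lesions per patient given small data available to date", but argues that "if only half of the positive patients have more than one lesion, this will easily yield 50 lesions". It concludes: "A sample size of 50 patients will provide 90% power at one-sided 5% error to detect such a difference". The sensitivities behind that statement are roughly 40% for MR alone and 60% or more for PET.

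No section mentions within-patient correlation, a clustered test, a robust variance or a patient-level test. Section 10.1 does expect a higher proportion of patients with detected lesions on PET/MRI than on MR, but attaches no test to it.

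**The concern.** McNemar's test takes its variance from the discordant pairs as if each pair were an independent observation. Here several pairs come from the same man, by design.

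What matters is the correlation, within a man, of the PET-minus-MR difference. An effect that raises or lowers detection on both methods alike largely cancels. An effect on PET alone does not: if a man's tumour expresses the tracer's target strongly or weakly at all sites, his lesions tend to fall on the same side of the comparison. Positive correlation of this kind makes the ordinary test reject too often; negative correlation would make it conservative.

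McNemar is the only test the plan names, so the one-sided 5% in 11.5 depends on it. Ordinary binomial intervals for per-lesion sensitivity, or for the predictive value in 10.4, would be too narrow whenever detection or malignancy is positively correlated within a man.

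**Working it through.** **Inputs from the plan (11.5).** One-sided 5%; power 90%; sensitivities 40% and 60%; about 35 men with lesions; half of them with more than one.

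**Assumptions, because the plan gives no value.**

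- Discordance between PET and MR, psi: 0.25, or 0.52 if the two are independent within a lesion (0.6×0.6 + 0.4×0.4).
- ICC, the within-man correlation of the PET-minus-MR difference: 0 to 0.5.
- Layouts of 35 men each:
  - 20×1 + 15×2 = 50 lesions.
  - 17×1 + 18×2 = 53, the least that half with more than one implies.
  - 17×1 + 18×3 = 71; the 3 is assumed.
  - 17×1 + 10×2 + 2×3 + 2×4 + 4×8 = 83, an illustrative skewed layout that is not in the plan.

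**1. The plan's own figure.** For n independent lesions and a difference of 0.2, power = Phi((0.2√n − 1.645√psi)/√(psi − 0.04)). With n = 50:

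- psi = 0.25: (1.414 − 0.823)/0.458 = 1.29, so 90.2%.
- psi = 0.52: (1.414 − 1.186)/0.693 = 0.33, so 62.9%.

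The stated 90% is therefore reproduced with 50 independent lesions at about 25% discordance. A one-sample test of 60% against a fixed 40% with 50 units gives 89.3%.

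**2. Expected inflation by formula.** Design effect D = 1 + ICC × (Σm²/Σm − 1), where m is the number of lesions per man. Actual error = 1 − Phi(1.645/√D).

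- 53 lesions: Σm²/Σm = 89/53 = 1.68. ICC 0.3: D = 1.20, error 6.7%. ICC 0.5: D = 1.34, error 7.8%.
- 71 lesions: 179/71 = 2.52. ICC 0.3: D = 1.46, error 8.6%. ICC 0.5: D = 1.76, error 10.8%.

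**3. Simulation under no difference** (40,000 trials per cell). Each lesion is PET-only, MR-only or concordant with probabilities (psi+d)/2, (psi−d)/2 and 1−psi, with d = 0. Each man's own probabilities are Dirichlet with total (1−ICC)/ICC. One-sided error at psi = 0.25:

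| Layout | Test | ICC 0 | 0.1 | 0.3 | 0.5 |
|---|---|---|---|---|---|
| 53 lesions | asymptotic | 5.1% | 5.6% | 6.7% | 8.0% |
| | exact | 2.9% | 3.3% | 4.0% | 5.0% |
| 71 lesions | asymptotic | 4.7% | 6.3% | 8.8% | 10.9% |
| | exact | 3.0% | 4.3% | 6.3% | 8.2% |
| 83, skewed | asymptotic | 4.8% | 7.5% | 12.2% | 15.8% |
| | exact | 3.2% | 5.4% | 9.8% | 13.2% |

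At psi = 0.52 with 53 lesions, ICC 0.3 / 0.5 gives asymptotic 6.5 / 7.9% and exact 4.8 / 6.1%. The Durkalski statistic, Σd_k/√Σd_k² with d_k the PET-only minus MR-only count in man k, held between 4.5% and 5.4% in every cell, including repeat runs.

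**4. Power of the Durkalski test** (d = 0.2, simulated):

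| Lesions, psi | ICC 0 | 0.3 | 0.5 |
|---|---|---|---|
| 53, 0.25 | 94.7% | 91.2% | 88.3% |
| 50, 0.25 | 93.6% | 90.1% | 87.4% |
| 53, 0.52 | 65.2% | 58.9% | 55.2% |

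Simulating 50 independent lesions at psi = 0.25 gives 94.3% (asymptotic) and 88.6% (exact), against 90.2% by formula, so losses are read within the simulation only. A cruder route, the one-sample formula with 53 lesions divided by D, gives 90.8%, about 86% and about 82% at ICC 0, 0.3 and 0.5.

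**5. Intervals.** Coverage of an unadjusted 95% Wilson interval for a 60% per-lesion sensitivity, with beta-distributed patient sensitivities and an ICC of detection of 0 / 0.3 / 0.5: 94.9 / 92.5 / 90.9% with 53 lesions, and 94.4 / 82.0 / 74.6% in the skewed layout. The correct width is larger by √D: √1.20 = 1.10 at 0.3 and √1.34 = 1.16 at 0.5 (53 lesions).

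**The case against.** The best counter-argument is that the harm is possible rather than shown, and small where the plan is most specific. The documents give no within-man correlation. With 53 lesions and 25% discordance the exact test does not exceed 5% even at ICC 0.5. The larger figures need more lesions per man than the minimum. This stands, but 11.5 itself says the number per man cannot be predicted, so the minimum cannot be relied on. The plan also does not choose the exact test.

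Second, 11.4.1 admits only PET/MRI-identified lesions. With both tracers taken together, a lesion seen on MR alone cannot enter, so the comparison favours PET before clustering matters, and a clustered test does not remove that. This also stands. The simulations count every lesion as malignant and let MR-only lesions be seen; they isolate the clustering effect and do not give this trial's actual error rate.

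Third, the McNemar sentence does not name the lesion, and a test on one pair per man would have no clustering. True, but 11.4, 11.4.1 and 11.5 all point to lesions, and no patient-level test is specified.

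Fourth, the primary outcome in 10.1 has no test, the one-sided 5% appears only in 11.5, and the plan specifies no confidence intervals. These points limit the consequence. The coverage figures describe what a default interval would do, not a method the plan chose.

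**Conclusion.** The concern holds in its conditional form. The design produces several lesions per man, and the named test ignores this. If the PET-minus-MR difference is positively correlated within a man, the error can exceed one-sided 5%. In the 53-lesion scenario at 25% discordance the excess is modest: at most 3.0 points for the asymptotic test at ICC 0.5, and none for the exact test. With 71 lesions both versions exceed 5% at ICC 0.3. Correlation, discordance and every layout beyond the minimum are assumptions.

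Clustering alone does not clearly overturn the 90% power: at 25% discordance the clustered test has roughly that in simulation, though the cruder formula puts it at about 82% to 86% for ICC 0.5 to 0.3. The unstated discordance matters more. This should be fixed because the correction is cheap; confidence is medium because the size depends on values the plan does not supply.

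**What to change.** - **11.4.2, test.** State that the lesion is the unit for comparing sensitivity and specificity. Replace the ordinary McNemar test with one clustered by patient, for example Durkalski.
- **11.4.2 and 10.4, intervals.** For per-lesion sensitivity, specificity and predictive values, report intervals from a patient-level robust variance or from a bootstrap that resamples patients.
- **11.5, power.** Attach the power to a number of lesions rather than to 50 patients. Restate it for the clustered test over a range of discordance, lesions per patient and within-patient correlation.

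The cost is wording and standard software, with no new data or patients. In the 53-lesion case at ICC 0.3 to 0.5, intervals widen by a factor of about 1.10 to 1.16. Compared with independent lesions, power falls by 3.5 to 6.4 points at 25% discordance (94.7% to 91.2% and 88.3%) and by 6.3 to 10.0 points at 52% (65.2% to 58.9% and 55.2%). The restriction to PET/MRI-identified lesions in 11.4.1 needs its own correction.
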